3.7 Center pooling strategy

The participants from lead-in study, MG0003, will be rolled over in this study. The data from all sites will be pooled for analyses purposes.

3.8 Coding dictionaries

Adverse events (AEs) and medical histories will be coded using version 24.0 or later of the Medical Dictionary for Regulatory Activities (MedDRA®).

Medications will be coded according to B3 version Mar 2021 or later of the World Health Organization Drug Dictionary (WHODD).

3.9 Changes to protocol-defined analyses

- The following two exploratory endpoints will not be analyzed as they have been removed from the MG program as a whole and have been included in the protocol in error:
 - Change from Baseline in the MG Symptoms PRO multicomponent total score, at each scheduled assessment during Treatment and Observation Periods,
 - Change from Baseline in the enhanced MG Symptoms PRO total score, at each scheduled assessment during Treatment and Observation Periods.
- The increase or reduction in use of concomitant medications will be analyzed in the SAP, so objective is changed to “To assess the dose change in use of concomitant medications in study participants receiving rozanolixizumab” in the SAP.

- The dose change in use of concomitant medications in study participants receiving rozanolixizumab will be analyzed using number and percentage of participants with dose change of concomitant medications and change from Baseline in ADD in the study. There is no concentration data of concomitant medications in the study to generate area under the curve (AUC), so it is not included in the SAP.
- No study participants from MGC003 will rollover into MG0004. Thus, the maximum sample size of this study should be 240, not 276.

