	
• Change from Baseline in the MG Symptoms PRO ‘Muscle Weakness Fatigability’ score at each scheduled assessment during Treatment and Observation Periods• Change from Baseline in the MG Symptoms PRO ‘Physical Fatigue’ score at each scheduled assessment during Treatment and Observation Periods• Change from Baseline in the MG Symptoms PRO ‘Bulbar symptoms’ score at each scheduled assessment during Treatment and Observation Periods• Change from Baseline in the MG Symptoms PRO ‘Respiratory symptoms’ score at each scheduled assessment during Treatment and Observation Periods• Change from Baseline in the MG Symptoms PRO ‘Ocular symptoms’ score at each scheduled assessment during Treatment and Observation Periods• Change from Baseline in the MG Symptoms PRO multicomponent total score, at each scheduled assessment during Treatment and Observation Periods• Change from Baseline in the enhanced MG Symptoms PRO total score, at each scheduled assessment during Treatment and Observation Periods• Change from Baseline in MGQoL15r at each scheduled assessment during Treatment and Observation Periods• Change from Baseline in EQ-5D-5L scores at each scheduled assessment during Treatment and Observation Periods 
For study participants who require rescue treatment during the Observation Period of MG0003 and subsequently enter MG0004, the following endpoints will be assessed:
 
• QMG responder rate (≥ 3.0 point improvement from Baseline) at each scheduled assessment during the first 6 weeks of the Treatment Period• MG-C responder rate (≥ 5.0 point improvement from Baseline) at each
--	--

	
scheduled assessment during the first 6 weeks of the Treatment Period
 
 • MG-ADL responder rate (≥ 2.0 point improvement from Baseline) at each scheduled assessment during the first 6 weeks of the Treatment Period
Other	
To assess the reduction in use of steroids in study participants receiving rozanolixizumab	
 • AUC of the oral steroid dose over time
To assess the plasma concentrations of rozanolixizumab administered by SC infusion	
 • Plasma concentration of rozanolixizumab at each scheduled assessment during the Treatment and Observation Periods

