6.4 Prior and concomitant medications

The number and percentage of participants taking Prior or Concomitant medications will be summarized using the RS by Anatomical Therapeutic Chemical (ATC) class, presenting as Anatomical Main Group (ATC Level 1), Pharmacological Subgroup (ATC level 3), Preferred Term (PT), treatment group and RLZ total. The number and percentage of participants taking steroids, Immunosuppressants and AChE Inhibitors will be summarized.

Additionally, rescue medications are those that are mentioned in Protocol section 6.5.3 and identified:

- if Rescue Medication is ticked as yes on CRF Concomitant Medication page
- Or PEX as procedure entered on CRF Concomitant Medical Procedure page

The start date of rescue medication should be on or after Baseline. All rescue medications will be summarized using the RS.

Medications classified as prior or concomitant will be listed using the RS. A by-participant listing of participants taking steroids, immunosuppressants and AChE Inhibitors will be listed, including ADD at Baseline, ADD at last study visit and change from Baseline in ADD (See [Section 11.1](#)). A by-participant listing of concomitant procedures will also be listed using the RS. Originally reported dates will be used for listings.

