6.4.1 Categories of prior and concomitant medications

Medications will be classified as follow based on imputed start and stop dates & times as outlined in [Section 4.2.2](#).

- **Prior** medications will include any medications that started before the first administration of IMP in MG0004.
- **Concomitant** medications will include any medications that have been taken at least once after the first administration of IMP during the Treatment and/or Observation Period of MG0004.

Medication Started	Medication finished	Classification
Before 1st Dose IMP	Any time	Prior
Any time	After 1st Dose IMP	Concomitant

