11 OTHER ANALYSES

11.1 Dose change in use of concomitant medications over time

The following summaries will be produced using SS in all participants:

- The number and percentage of participants with dose change in use of steroids (ATC3 code: █████), immunosuppressants (ATC3 code: █████) or AChE Inhibitor (ATC3 code: █████) during the study;
- Average daily dose (ADD) by PT of medications at Baseline and last study visit (i.e. PEOT/EOS visit);

Note: ADD will be calculated for each PT according to the dose and dose frequency on Prior and Concomitant Medications CRF (e.g. ADD of a participant taking steroid 20 mg QOD is 10 mg). Baseline ADD will follow the same Baseline definition in [Section 3.3](#), which will be calculated using the steroid dose taken prior to first IMP in MG0004. ADD at last study visit is calculated using the dose taken at EOS/PEOT visit. In the case last dose is stopped before EOS/PEOT visit, ADD at last study visit will be counted as zero.

- The change from Baseline of average daily dose (ADD) at last study visit, calculated as
ADD at last study visit – Baseline ADD;
- A listing will be provided for participants with dose change of steroids, including MG-ADL total score at Baseline and last study visit (EOS/PEOT visit), last MG-ADL score prior to first steroid dose change, maintenance dose of RLZ, Baseline steroid ADD and steroid ADD at last study visit.

Note: Maintenance dose of RLZ is the most recent dose of RLZ when last steroid dose is given.

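### SAP 3.9 drops the oral-steroid dose AUC for want of concentration data it does not need, so no summary gives cumulative or time-averaged steroid dose

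*SAP*

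**What the plan says.** Protocol section 3 (and the synopsis) sets an Other-tier objective of assessing the reduction in steroid use. Its single endpoint is "AUC of the oral steroid dose over time", with no period attached.

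SAP 3.9 widens the objective to dose change in concomitant medications and drops the AUC: "There is no concentration data of concomitant medications in the study to generate area under the curve (AUC), so it is not included".

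SAP 11.1 plans three summaries in its place: the number and percentage of participants with a dose change in steroids, immunosuppressants or AChE inhibitors; ADD at Baseline and at the last study visit (PEOT or EOS); and the difference between the two. On the source it says: "ADD will be calculated for each PT according to the dose and dose frequency on Prior and Concomitant Medications CRF". Its worked example turns 20 mg every other day into 10 mg. A listing for participants whose steroid dose changed shows "Baseline steroid ADD and steroid ADD at last study visit". The listing in SAP 6.4 uses the same two points, "including ADD at Baseline, ADD at last study visit and change from Baseline in ADD".

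**The concern.** The stated reason reads the endpoint as a pharmacokinetic AUC, whereas the protocol asks for an AUC of dose. If the inputs exist, a computable protocol endpoint is lost through a misreading.

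The replacement also measures something different. Protocol 6.5.1 sets no specific dose requirement for oral corticosteroids and allows dose adjustments during the study, so doses can move in either direction between Baseline and the last visit. The word average in ADD could suggest averaging over the study. In SAP 11.1 it means averaging over the dosing interval, and the last-visit value uses the dose taken at that visit. At stake is one descriptive result: how much oral steroid participants took while on rozanolixizumab.

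**Working it through.** **1. Are the inputs for a dose AUC available?**

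- Dose and frequency: on the Prior and Concomitant Medications CRF (SAP 11.1).
- Dates: SAP 6.4.1 classifies medications "based on imputed start and stop dates", and SAP 6.4 says "Originally reported dates will be used for listings".
- Frequency of recording: the Schedule of Activities (Protocol 1.3) marks concomitant medications at every visit column from Visit 1 to EOS.
- Dated dose changes: the SAP 11.1 listing needs the last MG-ADL score before the first steroid dose change, so it already assumes them.

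The SAP's own ADD example reproduces without concentrations: 20 mg / 2 days = 10 mg/day. The AUC takes one further step:

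dose AUC = sum of (daily dose x days at that dose); per-day value = AUC / days.

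**2. Does the two-point ADD change carry the same information?**

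The courses below are assumed. Each lasts 60 weeks (420 days), with Baseline ADD 20 and last-visit ADD 10 mg/day. SAP 11.1 would report the same result for all three: dose change yes, ADD change 10 - 20 = -10 mg/day.

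| Course | Dose AUC | Per day |
|---|---|---|
| A: 20 mg for 59 weeks, 10 mg for 1 week | 20 x 413 + 10 x 7 = 8,330 mg | 19.8 mg |
| B: 20 mg for 4 weeks, 10 mg for 56 weeks | 20 x 28 + 10 x 392 = 4,480 mg | 10.7 mg |
| C: 20 mg for 4 weeks, 40 mg for 52 weeks, 10 mg for 4 weeks | 20 x 28 + 40 x 364 + 10 x 28 = 15,400 mg | 36.7 mg |

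The range is 15,400 / 4,480 = 3.4-fold. Courses A and B involve no increase at any time and still differ 8,330 / 4,480 = 1.9-fold.

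**3. What are the limits of the AUC itself?**

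Raw AUC grows with follow-up. At a constant 20 mg/day it is 20 x 42 = 840 mg over 6 weeks and 20 x 420 = 8,400 mg over 60 weeks. Follow-up will differ, because Protocol 4.1 lets participants leave for MG0007 after a minimum of 6 visits.

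Dividing by days helps but does not remove the dependence on exit time. Take an assumed linear fall from 20 to 5 mg/day over 12 weeks, then held:

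| Exit | AUC | Per day (vs 20) | ADD change at exit |
|---|---|---|---|
| Week 6 | 42 x 16.25 = 682.5 mg | 16.25 (-18.75%) | 12.5 - 20 = -7.5 |
| Week 12 | 84 x 12.5 = 1,050 mg | 12.5 (-37.5%) | -15 |
| Week 26 | 1,050 + 98 x 5 = 1,540 mg | 8.46 (-57.7%) | -15 |
| Week 52 | 1,050 + 280 x 5 = 2,450 mg | 6.73 (-66.3%) | -15 |

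**The case against.** The best defence is that the replacement suits the objective. The protocol wants to know about reduction in steroid use. Change in ADD gives the size and direction of net change, as a planned summary and not only in listings. Raw AUC does not show reduction by itself and rises with follow-up. In the last table the ADD change is stable from week 12, while the per-day AUC keeps moving. The change is declared in SAP 3.9 with the objective reworded, and medications are listed with reported dates. The protocol gives the AUC no period, so any window is the analyst's choice.

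All of this stands, and it limits the severity and shapes the fix. It does not rescue the reason given in 3.9, and it does not supply a summary of cumulative or time-averaged dose.

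A reader might go further and infer that the ADD change is unusable because it pools readings at different times: PEOT for participants leaving the Treatment Period for MG0007, and EOS at Week 60 for completers. The documents do not support that. SAP 11.1 names the visit, and net change to each participant's last visit is a legitimate description. Splitting it by visit type is a preference.

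**Conclusion.** The point holds at low severity. SAP 3.9 removes a computable protocol endpoint on a rationale that does not apply to it. What remains describes net change between two points and not the amount of steroid taken.

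Two stronger inferences should be resisted. This is not an undisclosed deviation, because 3.9 states it openly. It does not touch the primary safety or secondary efficacy results: the endpoint sits in the Other tier, and the SAP plans no statistical testing.

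The conclusion rests on reading the endpoint as an area under dose, which is what its wording says, and on the CRF holding dated dose records, which SAP 6.4, 6.4.1 and 11.1 presuppose. The 1.9-fold and 3.4-fold figures come from assumed courses. They show what an identical ADD change can conceal, not what will happen in this trial.

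**What to change.** - In SAP 3.9, delete the concentration rationale. If the AUC is still not wanted, give a valid reason there.
- Otherwise add to SAP 11.1 an oral-steroid dose AUC (sum of daily dose x days) from first IMP over a stated window, for example to Week 52/PEOT. Label the window as an analysis choice, because the protocol states none.
- Report it also per day against Baseline daily dose. Note that the per-day value still depends on exit time, and show participants reaching Week 52, or a common early window, alongside all participants. The cut-points in SAP 8.1 should not serve as strata: they are cumulative, overlapping thresholds of IMP duration.
- State a dose-equivalence conversion if more than one oral steroid is used, since ADD is calculated separately for each preferred term.
- Extend the partial-date rule in SAP 4.2.2 to this derivation. For medications it currently covers classification only.

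The cost is SAP wording, one derived variable from data already collected, a conversion table if needed, and a small amount of programming. No new data collection is required.

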4 STATISTICAL/ANALYTICAL ISSUES

4.1 Adjustments for covariates

Statistical testing is not planned for this study, hence adjustment for covariates will not be required.

4.2 Handling of dropouts or missing data

4.2.1 Efficacy data

The rules for handling missing data of individual items in the calculation of the QMG, MG-C, MG-ADL, MG Symptom PRO, MGII and MG-QOL15r scores are described in [Section 13.1](#), [Section 13.2](#), [Section 13.3](#), [Section 13.4](#), [Section 13.5](#), and [Section 13.6](#), respectively.

For ordinal endpoints (e.g. EQ-5D-5L), the complete case method will be applied. No further imputation is used.

4.2.2 Dates and times

Partially or completely missing dates may be imputed for the following reasons:

- Classification of AEs as TEAEs;
- Classification of medications as past, prior, or concomitant medications;
- Durations of AEs.

Imputed dates will not be shown in listings. All dates will be displayed as reported in the database.

The following rules will be applied for partially or completely missing start dates:

- If year, month and day are all missing then assign the date of first dose of IMP. If an imputed start date is after the specified end date, then assign January 01 of the year of the end date, or the date of screening if this is later (if the latter imputation results in an end date that is earlier than the start date, then use January 01).
- If month and day are missing, and year is:
 - the same as the year of the first dose of IMP then assign the month-day of first dose of IMP. If the imputed start date is after the specified end date, then assign January 01, or the month-day of screening date if this is later (if the latter imputation results in an end date that is earlier than the start date, then assign January 01);
 - not the same as the year of the first dose of IMP then assign January 01.

- If only day is missing, and month-year is:
 - the same as the month-year of the first dose of IMP then assign the day of first dose of IMP. If the imputed start date is after the specified end date, then assign first day of the month, or the day of screening date if this is later (if the latter imputation results in an end date that is earlier than the start date, then assign first day of the month);
 - not the same as the month-year of the first dose of IMP then assign the first day of the month.

The following rules will be applied for partially or completely missing stop dates:

- If only the month and year are specified, then use the last day of the month. If an imputed stop dates is after last contact date, then assign last contact date as the stop date;
- If only the year is specified, then use December 31 of the known year. If an imputed stop dates is after last contact date, then assign last contact date as the stop date;
- If the stop date is completely unknown, then use discharge date or data cut-off date. Discharge date refers to the date of the end of study visit for completed participants or the date of discontinuation for participants that were withdrawn. For any AEs with known start date after the date of discontinuation, the date of last contact will be used as the discharge date. For participants still ongoing in the study at the time of the data cut-off, and for whom no discharge date is available, the date of the data cut-off will be used instead of the discharge date.

Any medication with a start date on the first dosing date and time unknown, will be assumed to be concomitant.

Imputed AE dates will be used for the calculation of duration of AEs as described in [Table 4-1](#).

Table 4-1: Calculation rules for duration of AEs

Data availability	Onset date	Outcome date	Calculation rules
Complete data	D1	D2	Duration = D2 – D1 + 1 d
Start date partially or completely missing	--	D2	Duration = < D2 – D0 + 1 d Notes: D0 is imputed start date per above rules.
End date partially or completely missing	D1	--	For ongoing AE: Duration = > D3 – D1 d For resolved AE: Duration = < D3 – D1 d Notes: D3 is imputed end date per above rules.

Table 4–1: Calculation rules for duration of AEs

Data availability	Onset date	Outcome date	Calculation rules
Start and end date partially or completely missing	--	--	For ongoing AE: Duration = >D3 – D0 d For resolved AE: Duration = < D3 – D0 d Notes: D0 is imputed start date and D3 is imputed end date per above rules.

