8.2.3 Adverse events of focus

Rozanolixizumab adverse events of focus (AEOF) include the following categories:

- Headaches
- Gastrointestinal disturbances
- Hypersensitivity reactions
- Anaphylactic reactions
- Injection site reaction
- Infusion reaction
- Infections
- Opportunistic infections
- Reductions in albumin and plasma proteins
- Effects on the kidney
- Drug related hepatic disorders
- Effects on lipids

1. The number and percentage of study participants who experience each category of the AEOF will be summarized by most recent dose level prior to onset of the AEOF and RLZ total treatment group. The following summaries will be presented by SOC, HLT, and PT:

- AEOF
- Serious AEOF
- AEOF by relationship
- AEOF by maximum intensity (mild, moderate and severe)

2. Additionally, the summaries for the AEOF headache and gastrointestinal disturbances in Treatment Period by intensity will be presented separately by most recent dose level and RLZ total.

3. Graphs for AEOF headache in Treatment Period by time of onset (relative to infusion), severity, causality and duration for each study participant will also be provided.

A by-subject listing of all AEOF by category (as listed above) will be provided by treatment group and participant. Most recent dose will be presented in listing even when the AE start date is partial. Further details related to the statistical analysis of the above mentioned treatment-emergent AEOFs are provided in [Section 13.8](#).

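### SAP Table 4-1 draws upper and lower AE-duration bounds from one imputed start date, so the bound for ongoing AEs with a partial start prints roughly the maximum as a minimum

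*SAP*

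**What the plan says.** SAP 4.2.2 gives a single set of start-date imputation rules that serves TEAE classification, medication classification and AE duration. D0 depends on what was recorded:

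- Start wholly missing: "If year, month and day are all missing then assign the date of first dose of IMP".
- Year only, in the first-dose year: "the same as the year of the first dose of IMP then assign the month-day of first dose of IMP".
- Day missing, in the first-dose month: "the same as the month-year of the first dose of IMP then assign the day of first dose of IMP".
- Any other month or year: the first of that month, or 1 January.
- If a first-dose imputation falls after the recorded end date, D0 drops back to the first of the month or 1 January, or to screening if that is later.

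Table 4-1 then states that "D0 is imputed start date per above rules" and uses it three ways:

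- Start incomplete, end known: "Duration = < D2 – D0 + 1 d".
- Both incomplete, resolved: "For resolved AE: Duration = < D3 – D0 d".
- Both incomplete, ongoing: "For ongoing AE: Duration = >D3 – D0 d".

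With complete dates the duration is end minus start plus 1.

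SAP 8.2.1 collects AEs from consent, counts a pre-dose event that worsens as a TEAE, and keeps persistent MG0003 events in the database as non-TEAEs that are only listed. The one output that names AE duration is in SAP 8.2.3: "Graphs for AEOF headache in Treatment Period by time of onset (relative to infusion), severity, causality and duration for each study participant".

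**The concern.** A printed `<` duration is true only if it is measured from the earliest start the record allows. A printed `>` duration is true only if it is measured from the latest. D0 was built for neither purpose. It follows a conservative convention that pulls undated events to first dose so that they count as treatment-emergent.

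In the ongoing row, D0 outside the first-dose month or year is the earliest possible start, so D3 − D0 is close to the longest elapsed time and is labelled as the shortest. In the upper-bound rows, a D0 at first dose or at screening is too late for an AE that began earlier.

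What is at stake is the description of how long events lasted. Headache is where this matters most: Protocol 10.20.1 describes it as the adverse reaction reported most often with rozanolixizumab, and its duration is plotted participant by participant.

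**Working it through.** The plan states no figure to reproduce. The check applies the 4.2.2 rules and the Table 4-1 formulas to assumed dates, then compares the printed bound with every duration the recorded dates allow. True duration is end − start + 1, as in the complete-data row. For ongoing AEs it is the time elapsed to D3.

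**Assumed participants.** A: first dose 15 Jun 2020. B: first dose 20 Mar 2021, screening 13 Mar 2021.

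**Lower bound: both dates incomplete, AE ongoing (prints > D3 − D0)**

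| Recorded start | D3 | D0 | Printed | Elapsed time possible |
|---|---|---|---|---|
| A: Mar 2021 | 31 Mar 2021 | 1 Mar 2021 | `>30 d` | 1 to 31 d; onset 30 Mar gives 2 d |
| B: May 2021 | 30 Jun 2021 | 1 May 2021 | `>60 d` | 31 to 61 d |
| B: wholly missing | 30 Jun 2021 | 20 Mar 2021 | `>102 d` | 1 to 103 d, even if the start was on or after first dose |

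For B's May start, `>60 d` is not established for 30 of the 31 possible onset days. No pre-dose onset is needed for this row to fail.

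The row with a known start is sound: start 10 May 2021, ongoing at 30 Jun 2021, prints `>51 d`, and 52 d have elapsed.

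**Upper bound: incomplete start (end known: prints < D2 − D0 + 1; both incomplete and resolved: prints < D3 − D0)**

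| Recorded start | End | D0 | Printed | Duration possible |
|---|---|---|---|---|
| A: Jun 2020 | 1 Jul 2020 | 15 Jun 2020 | `<17 d` | up to 31 d |
| A: 2020 | 1 Jul 2020 | 15 Jun 2020 | `<17 d` | up to 183 d |
| B: Mar 2021 | 25 Mar 2021 | 20 Mar 2021 | `<6 d` | 1 to 25 d; 19 of 25 starts exceed 6 d |
| B: Mar 2021 | 18 Mar 2021 | 13 Mar 2021 (screening) | `<6 d` | 1 to 18 d; 12 of 18 starts exceed 6 d |
| B: Mar 2021, resolved | May 2021 (D3 31 May) | 20 Mar 2021 | `<72 d` | 32 to 92 d; 210 of 961 date pairs exceed 72 d |
| B: May 2021 | 25 May 2021 | 1 May 2021 | `<25 d` | 1 to 25 d; none exceeds 25 d, one equals it |

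The counts give each possible date equal weight. They show what the record permits and are not estimates of how often the bound would be wrong. In the rows with a known end and D0 at first dose, every start that exceeds the bound lies before first dose. If the start is restricted to first dose or later, the longest duration equals the printed number, so only strict `<` fails.

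**Missing +1.** Start 10 May 2021, end recorded as May 2021, resolved: D3 is 31 May, and D3 − D1 prints `<21 d`. The true maximum is 21 + 1 = 22 d. The statement is false if the AE ended on 30 or 31 May.

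**The case against.** The best defence is that one imputed start for all purposes is openly stated and keeps each event's emergence and duration consistent. That is a reasonable choice for a point value. It does not justify printing an inequality the record cannot support.

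The defence does limit the upper-bound half. Under SAP 13.8 a headache of focus must be a TEAE, and under SAP 8.2.1 a Treatment Period TEAE must start on or after first dose. For events that truly did so, the first-dose date is the earliest start. A reader might infer that persistent MG0003 headaches distort the graphs through these rows. The documents do not support that, because persistent events are non-TEAEs that are only listed. A pre-dose headache gets in only if its incomplete date lets it default to treatment-emergent. The 183 d example almost certainly needs an event carried over from MG0003, and the 31 d example probably does.

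A reader might also infer that AE listings will show false durations. No section says that listings carry AE duration, and 4.2.2 displays dates as reported.

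Frequency should be low. Dosing-period visits are weekly, AEs are recorded at each one (Protocol 1.3 and 4.1), and severe or serious headache triggers a daily questionnaire (Protocol 10.20.1).

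None of this reaches the ongoing row, which fails without any pre-dose onset.

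**Conclusion.** The point holds as a minor error in a stated rule. The main fault is the row with both dates incomplete and the AE ongoing. It prints about the maximum elapsed time as a minimum when the start lies outside the first-dose month or year, and it gives no valid minimum when the start is wholly missing.

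The upper-bound rows are wrong by more than a day or so only for AEs that began before first dose, which SAP 8.2.1 allows. For the rest the fault is strict `<` at equality, plus the dropped +1 in the resolved rows with an incomplete end date.

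The effect is confined to descriptive durations of AEs with incomplete dates. The stronger reading, that safety conclusions are at risk, is not supported: TEAE counts, TEAE classification and both primary endpoints are unchanged. The numerical examples rest on assumed dates. The documents do not say how many AEs will have incomplete dates or how a bound will be drawn on the headache graphs.

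**What to change.** Revise Table 4-1 as follows:

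- Upper bounds: ≤ latest possible end − earliest possible start + 1. The earliest start is the first of the recorded month, or 1 January of the recorded year.
- Lower bounds for ongoing AEs: ≥ D3 − latest possible start + 1. The latest start is the last day of the recorded month or year, and no later than D3.
- Start wholly missing: print no numeric bound.
- Keep D0 for TEAE classification.

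Under these rules:

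- B's March start ending 25 Mar 2021 becomes ≤25 d (25 − 1 + 1).
- B's March-to-May resolved AE becomes ≤92 d (1 Mar to 31 May inclusive).
- B's May start ongoing at 30 Jun 2021 becomes ≥31 d (31 May to 30 Jun inclusive).
- A's March 2021 start ongoing at 31 Mar becomes ≥1 d.

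The cost is a table edit and a few lines of code. There is one small downside: an event's start for duration can differ from its start for TEAE classification, so a treatment-emergent event may carry pre-dose days in its upper bound. A footnote to Table 4-1 and to the headache graphs should say so.

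### SAP Table 4-1 omits the +1 day for a resolved AE with known onset and an imputed end date, so the upper bound on duration can be one day short (two if the sign is strict)

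*SAP*

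**What the plan says.** SAP Section 4.2.2 lists AE duration among the purposes of date imputation, and Table 4-1 gives the formulas.

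- Complete dates: "Duration = D2 – D1 + 1 d".
- Start missing, with D0 the imputed start: "Duration = < D2 – D0 + 1 d".
- End missing, with D3 the imputed end: "For resolved AE: Duration = < D3 – D1 d" and "For ongoing AE: Duration = > D3 – D1 d".
- Both missing, resolved: "For resolved AE: Duration = < D3 – D0 d".

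The same section fixes D3. For a partial date, "If only the month and year are specified, then use the last day of the month"; if only the year is known, 31 December is used. Both are capped: "If an imputed stop dates is after last contact date, then assign last contact date as the stop date". A completely unknown stop date takes the discharge date or the data cut-off date.

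Section 8.2.3 uses duration in one named display: "Graphs for AEOF headache in Treatment Period by time of onset (relative to infusion), severity, causality and duration", drawn for each participant.

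**The concern.** The complete-data row sets an inclusive count, in which an event that starts and ends on the same day lasts one day. The start-missing row keeps that count. The two resolved cells with an imputed end date do not, and Section 4.2.2 gives no reason. The SAP counts inclusively elsewhere too: study IMP duration in Section 8.1 adds one day, as does relative day on or after first infusion in Section 3.2.1.1.

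For a resolved event with a month-only or year-only end date, D3 is the latest day on which the event can have ended. The cell is therefore an upper bound on duration, and an upper bound must allow the longest duration that the table's own complete-data rule can produce. This one does not, and in the extreme case it prints an impossible value. What is at stake is the correctness of some reported durations, chiefly in the headache graphs. Protocol Section 10.20.1 names headache as the most commonly reported adverse drug reaction.

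**Working it through.** **Inputs.** All come from SAP Section 4.2.2: the inclusive rule for complete dates, the resolved-event rule with D3, and D3 set to the last day of the month when only month and year are known.

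**Longest possible duration.** With onset D1 and true end E no later than D3, the complete-data rule gives E − D1 + 1. The maximum, at E = D3, is D3 − D1 + 1.

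**What the cell allows.**
- Strict sign: the largest whole number below D3 − D1 is D3 − D1 − 1. The shortfall is (D3 − D1 + 1) − (D3 − D1 − 1) = 2 days if the event ended on D3, and 1 day if it ended on D3 − 1.
- Sign read as at most: the largest value is D3 − D1. The shortfall is 1 day, and only if the event ended on D3.

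**Examples, end date reported as June, D3 = 30 June.**

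| Onset | Table prints | Possible true duration |
|---|---|---|
| 10 June | `<20 d` | 1 to 21 days |
| 29 June | `<1 d` | 1 or 2 days |
| 30 June | `<0 d` | 1 day |

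The last row also arises whenever the cap sets D3 to a last contact date equal to the onset date.

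**Enumeration.** A 30-day month has 30 × 31 / 2 = 465 pairs of onset day and end day on or after it. These are counts of possibilities, not probabilities.
- Current rule, strict sign: the pairs ending on day 30 (30 of them, 2 days short) and on day 29 (29 of them, 1 day short) break the bound, so 59 of 465.
- Current rule, sign read as at most: 30 of 465 break it.
- +1 restored, strict sign kept: 30 of 465 still break it, each by 1 day, and D1 = D3 prints `<1 d` for a 1-day event.
- `<= D3 – D1 + 1`: 0 of 465 break it, and the smallest bound is 1 day.

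The 28-day and 31-day months show the same pattern: 55 of 406 and 61 of 496 under the current strict rule, and 0 after the full repair.

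**Ongoing events, known onset.** An event still ongoing at D3 has lasted at least D3 − D1 + 1 days, which exceeds D3 − D1. That rule is sound. Reversing its sign without adding the day does not give a valid upper bound.

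**The case against.** **The two-day figure depends on the sign.** The table prints an equals sign followed by a less-than sign, which could loosely mean at most. That stands. The missing +1 accounts for one day, and the second appears only under a strict reading. The looser reading does not rescue the cell, because it still gives at most 0 days when D1 = D3.

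**Short headaches.** A reader might infer that durations of short headaches are generally understated by about their own length. The documents do not support this. With a month-only end date, D3 is month-end, so the bound is usually far too long, as in the 10 June example. Among events of 1 to 3 days (an illustrative range, not a figure from the documents) in a 30-day month without the cap, there are 30 + 29 + 28 = 87 onset/end pairs. Only the 6 ending on day 29 or 30 break the strict bound, about 7%.

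**The start-missing row.** A reader might also infer that this row merely needs `<=` because D2 − D0 + 1 is its attainable maximum. That does not hold in general, because D0 is not always the earliest possible start. Section 4.2.2 normally assigns the first-dose date when the start is wholly missing or its known part matches first dose. With first dose on 15 June, start reported as June and end on 20 June, D2 − D0 + 1 = 6 days, yet a true start on 3 June gives 18. The same limit applies when both dates are missing.

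**D3 is not always the latest date.** For a completely unknown stop date, last contact replaces the discharge date only for AEs that start after discontinuation. An AE that began before discontinuation could resolve after D3. This stands, and it is why the claim is confined to month-only and year-only end dates.

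**Practical reach.** AEs are recorded at every visit, and visits are weekly in the Treatment Period (Protocol Sections 1.3 and 4.1). Severe or serious headaches have a daily questionnaire until resolving or resolution (Protocol Section 10.20.1). Partial end dates for headache should therefore be uncommon, although the documents give no count.

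**Conclusion.** The rule for a resolved AE with known onset and an imputed end date is inconsistent with the table's own day count, and nothing elsewhere in the SAP corrects it. For month-only or year-only end dates the bound is one day too short when the event ended on D3. Under a strict sign it is two days short for an end on D3 and one day short for an end the day before. It prints `<0 d` when D1 = D3. The resolved cell with both dates missing has the same omission, but there the repair only makes the day count consistent and does not guarantee a maximum.

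This is a minor point. It touches only reported durations of resolved AEs with partial or missing end dates, and Section 8.2 names no display of duration other than the headache graphs. TEAE counts, TEAE classification and the primary endpoints do not depend on this formula. The conclusion assumes that the complete-data row defines the intended day count.

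**What to change.** In Table 4-1:

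1. Resolved AE, end date missing: `Duration <= D3 – D1 + 1 d`. Both the +1 and the non-strict sign are needed.
2. Resolved AE, both dates missing: `Duration <= D3 – D0 + 1 d`, for a consistent day count.
3. Add a footnote that durations using D0 are not guaranteed maxima, because D0 may be the first-dose date, and that D3 may precede the true end when the stop date is completely unknown.
4. Leave the ongoing-AE rule unchanged.

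The cost is two cells, one footnote and the matching lines of the derivation program. Data collection is unaffected.
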